### **Secondary Objectives**

1. Quantify the amount of tumor necrosis before and after initial treatment in both groups by CT volumetry, and correlate with response to treatment by RECIST criteria.
2. Evaluate toxicity, time to progression (TTP) and survival in each treatment arm.  
Determine if initial imaging response to treatment, as manifested by either RECIST criteria or volume of necrosis correlates with either TTP (by RECIST or volumetric method) or survival.

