A microscopic bead has been developed that can be used as an embolic agent alone, or loaded with doxorubicin to deliver high concentration of the drug to a target tumor within the liver while limiting systemic exposure. Before this agent that is much more expensive than conventional embolic material comes into widespread use, it would be valuable to assess its effectiveness. Since the agent is itself an embolic and can be used without loading doxorubicin, the opportunity exists to determine to what extent the addition of chemotherapy enhances the effect of embolization alone. Although survival is clearly the most important endpoint in evaluating treatments for HCC, survival studies require several years of follow-up in these patients, whereas preliminary data regarding response to treatment can be obtained using imaging. Traditionally, Response Evaluation Criteria In Solid Tumors (RECIST) have been used to evaluate response to treatment, and will be used as a primary endpoint in this study. These criteria are based on the product of bi-dimensional orthogonal measurements of a treated lesion, and do not take into account the degree of tumor necrosis resulting from treatment. The Barcelona-2000 EASL conference [Bruix J, et al 2001] concluded that tumor necrosis is an important indicator of

response to treatment for HCC, and recommended that changes in viable tumor area, rather than overall tumor area, be used to assess response. RECIST criteria have been found to be insensitive when used to evaluate other tumors that develop significant necrosis in response to treatment, such as the response of GIST tumors to Imatinib [Benjamin RS, et al 2006]. In this study, % tumor necrosis will serve as a secondary endpoint. Tumor necrosis will be quantified on contrast enhanced CT scans using an automated volumetric method, and the relationship of tumor necrosis to response as measured by RECIST criteria will be determined. These 2 measures of response to treatment will be correlated with TTP and survival in an attempt to establish the utility of one or the other as a surrogate outcome marker.

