## **12.0 CRITERIA FOR THERAPEUTIC RESPONSE/OUTCOME ASSESSMENT**

All patients will undergo contrast enhanced triple phase CT within 6 weeks of registration and then again within 2-3 weeks of completing their first treatment. Prior to treatment index lesions according to RECIST will be identified and conventional uni-dimensional measurements obtained blinded to the patients treatment group assignment. Response to treatment will be assessed by conventional RECIST criteria (see **Section 4.1**). The electronic data will then be sent to an independent imaging laboratory where an imager not familiar with the same patient's initial data set will create a volumetric profile including volume of tumor and volume of necrosis at time 0. On the initial post-treatment scans the index tumor(s) will once again be identified and measured by an imager blinded to the patient's treatment group, and once again the electronic data will be sent to the imaging laboratory where it will be independently analyzed volumetrically, once again recording tumor volume, and volume of necrosis. These results will be recorded in the electronic database. These linear and volumetric assessments will be repeated each time the patient is imaged for the duration of the study. Any increase in standard manual measurements of >20%, or the development of > 75% increase in enhancing tumor volume will be considered evidence of progression of disease (PD) and so recorded. In addition, patients who develop  $\leq 5\%$  necrosis, by volume, following the initial treatment, or increase of >50% in sum of uni-dimensional measurements following subsequent treatments will be considered treatment failures.

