Another secondary objective is to establish whether the use of the doxorubicin eluting beads might prolong time to progression (TTP), or survival, and if initial imaging response to treatment, as manifested by necrosis, correlates with either endpoint. This aim relates to analysis with censored outcomes (time-to-progression and survival time). We will use the Kaplan-Meier method to estimate the survival probabilities and we will use the log-rank test to compare groups. With 50 patients in each arm, we will have approximately 80% power to detect a hazard ratio of 3, assuming a median follow-up of 3 years (i.e., about half of the patients expiring) and controlling the Type I error rate at 5%. A hazard ratio of 3 corresponds to improving the median survival by three-fold or improving two-year survival by approximately 20%. We do not anticipate a survival difference of this magnitude so this aim will primarily serve to obtain preliminary data to plan a future definitive trial.

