### Appendix 3. Okuda Staging

Tumor size >50%	“+”
Ascites clinically detectable	“+”
Albumin <3 g/dl	“+”
Bilirubin > 3	“+”
Stage I	no positive indicators
Stage II	1-2 positive indicators
Stage III	3-4 positive indicators

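### The aim relating imaging response to progression and survival names no adjustment for baseline tumor burden or treatment arm, so its result may be confounded in either direction

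*Combined protocol and SAP*

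**What the plan says.** The aim appears in several places. The Secondary Objectives in Section 2.0 read: "Determine if initial imaging response to treatment, as manifested by either RECIST criteria or volume of necrosis correlates with either TTP", or survival. Section 3.0 (Preliminary Data) says "These 2 measures of response to treatment will be correlated with TTP and survival", with a view to choosing one of the measures as a surrogate. Section 14.0 restates the aim for necrosis only: "if initial imaging response to treatment, as manifested by necrosis, correlates with either endpoint".

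For censored outcomes the methods given are these: "We will use the Kaplan-Meier method to estimate the survival probabilities and we will use the log-rank test to compare groups". No section names a regression model, covariate, stratified test or landmark time for this aim.

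Burden is measured. In Section 12.0 the imaging laboratory "will create a volumetric profile including volume of tumor and volume of necrosis at time 0". Section 6.2 excludes patients only when more than 75% of the liver is replaced by tumor. Appendix 3 lists "Tumor size >50" percent as one of four adverse Okuda indicators, and Section 6.1 admits stages I and II. Randomization is stratified by whether one or two embolization sessions are expected (Sections 8.0 and 9.0), but that factor is not carried into this analysis.

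**The concern.** Randomization makes the two arms comparable. It does not make responders comparable with non-responders, because response is observed after treatment and may depend on the tumor the patient started with. Stratifying the allocation by expected sessions balances the arms on a rough proxy for extent and does nothing for this comparison.

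Confounding needs burden to be linked both to prognosis and to imaging response. The protocol supports the first link through Okuda staging and admits a wide range of burden. If the second link exists, a marker that adds nothing to baseline size can look predictive. If it runs the other way, a useful marker can look useless. Leaving treatment arm out raises a similar problem, since any arm effect on both response and survival would enter the marker's apparent effect.

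At stake is the reading of a result that Section 3.0 hopes may help validate an imaging technique and indicate whether it could serve as a surrogate. This is bias, so more patients would not cure it.

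**Working it through.** **The plan's own figure.** The plan gives no figure for the marker aim. The nearest is about 80% power for a hazard ratio of 3 with 50 patients per arm and about half of the patients dying. By Schoenfeld's formula with 50 deaths, √(50 × 0.25) × ln 3 − 1.96 = 3.884 − 1.96 = 1.92, which is 97% power, so the 80% does not reproduce. That is a separate matter about the arm comparison. Only the count of about 50 deaths is used here.

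**Inputs from the documents.** 100 patients; about 50 deaths (Section 14.0); 3-year survival of 42% in the institution's earlier series (Section 3.0).

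**Assumed inputs.** Correlation ρ of 0.1 to 0.5 in absolute value between baseline log volume and percent necrosis; death hazard ratio of 1.5 to 2.0 per SD of log volume; two-sided 5% test; no true effect of necrosis on survival.

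**Approximation.** With volume left out, the spurious log hazard ratio per SD of necrosis is about b = ρ × ln(HR). Its standard error is about 1/√50 = 0.141. With z = b/0.141, the chance of declaring an effect is Φ(z − 1.96) + Φ(−z − 1.96). Larger tumors are taken to show less necrosis.

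| ρ | HR per SD volume | b | Spurious HR | z | Approximate rate | Simulated rate (HR) |
|---|---|---|---|---|---|---|
| 0.1 | 1.5 | 0.041 | 0.96 | 0.29 | 6% | 5-7% |
| 0.1 | 2.0 | 0.069 | 0.93 | 0.49 | 8% | 5-7% |
| 0.2 | 1.5 to 2.0 | 0.081 to 0.139 | 0.92 to 0.87 | 0.57 to 0.98 | 9% to 17% | 8-17% |
| 0.3 | 1.5 | 0.122 | 0.89 | 0.86 | 14% | 13-15% (0.89) |
| 0.3 | 2.0 | 0.208 | 0.81 | 1.47 | 31% | 25-27% (0.83) |
| 0.5 | 1.5 | 0.203 | 0.82 | 1.43 | 30% | 30-32% (0.82) |
| 0.5 | 2.0 | 0.347 | 0.71 | 2.45 | 69% | 59-65% (0.73) |

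The simulated column is an unadjusted Cox model on continuous necrosis (100 patients, exponential survival, censoring uniform over 2 to 4 years, 52 to 58 deaths). The spans are the spread over repeated runs. A log-rank split at the median gives 11% to 46% for ρ of 0.3 to 0.5.

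**With adjustment.** Adding baseline volume and arm returns the hazard ratio to about 1.0 and the false-positive rate to 4-7%. For ρ of 0.3 to 0.5 the standard error rises by about 7-17%. Correlation alone would give 1/√(1 − 0.09) = 1.05 to 1/√(1 − 0.25) = 1.15.

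**Reversed sign.** If larger tumors showed more necrosis, the weakest ρ = 0.3 case would give exp(+0.122) = 1.13 (1.11 by simulation), which would mask a real benefit.

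**Binary response.** With 15% responders (assumed), the four scenarios at ρ of 0.3 and 0.5 give only 7% to 20%. With burden and response both binary, response rates of 50% in small and 20% in large tumors and a burden hazard ratio of 2 give a spurious hazard ratio of 0.80 and a 10% rate. Over all the binary scenarios tried, the rate was 4% to 61% unadjusted and 4-6% adjusted. TTP was not simulated.

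**The case against.** The strongest objection is that half of the mechanism is assumed. A reader might infer that the protocol shows smaller tumors respond more fully. It does not. Section 2.0 says there are no historical imaging-response data for either group. Under Section 9.0 both arms are embolized toward stasis in each feeding vessel, so the embolic volume scales with the tumor. The response CT follows the complete treatment, so staging does not mean undertreatment. The fixed 150 mg applies to one arm and to each procedure. Section 3.0 notes, for conventional chemoembolization, that full delivery can fail in smaller tumors. All of this stands: neither the link nor its sign is documented, and with a weak link the error rate stays near 5%.

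The plan is also looser than it might seem. A reader might infer that the arms will be pooled, or that the log-rank test is definitely the marker analysis. Section 14.0 says only "we will use the log-rank test to compare groups", in a paragraph whose power statement concerns the arms, and the 50% necrosis cut-off is given only for agreement with RECIST. Nor does the protocol promise to declare a surrogate. Its wording is tentative, and Section 14.0 describes the TTP and survival aim as mainly preliminary data for a later trial. That limits the harm. It does not supply an analysis, and silence leaves covariates to be chosen after the data are seen.

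Finally, adjustment is not a complete cure. Section 12.0 itself describes automated segmentation as very hard. With an assumed measurement error of 0.7 SD in volume and the strongest scenario, adjusting for volume still leaves a hazard ratio of 0.88 and 12% false positives.

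**Conclusion.** The point holds in conditional form. The imaging-response aim compares non-randomized groups, and the plan names no adjustment for baseline burden or arm. If burden affects imaging response, the unadjusted association is biased, and the bias may create or hide a marker effect.

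The size depends on an assumption the documents cannot settle. For necrosis and survival it runs from about nominal (5-7% at a correlation of 0.1) to about 60% (correlation 0.5, hazard ratio 2.0 per SD). Quoting only the upper part of that range would overstate the case. The rate is lower for an infrequent binary response, and no figure is offered for TTP.

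This is a worthwhile, inexpensive improvement to an exploratory secondary aim. The primary objective, estimating response rates by arm, is untouched.

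**What to change.** In Section 14.0, for this aim only:

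- Specify Cox models for survival and for TTP, with time starting at the response CT (a landmark). Section 4.1 times local progression from randomization, before imaging response is known. Leave out, and count, patients who have died or, for TTP, progressed by that scan.
- Include the imaging measure (necrosis as a continuous variable; RECIST response in a separate model), baseline log tumor volume of the measured lesions, and treatment arm. Add the one/two-session stratum and Okuda stage only as the number of events allows.
- Report adjusted beside unadjusted hazard ratios with 95% confidence intervals, and base any statement about marker utility on the adjusted result.
- State that an adjusted association is preliminary and does not by itself establish surrogacy.

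The cost is a paragraph of analysis text and a few lines of code. Volume profiles of the index lesions, arm, stratum and staging are already part of the study. Section 12.0 refers to index lesions, so the covariate should not be described as total liver tumor volume. The price is a somewhat wider interval (standard error about 7-17% larger at correlations of 0.3 to 0.5) and possible residual confounding from error in measured volume.

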## 1.0 PROTOCOL SUMMARY AND/OR SCHEMA

Purpose:	The objective of this study is to evaluate hepatic arterial embolization for hepatocellular cancer using microscopic beads and the same microscopic beads loaded with doxorubicin.
Study design:	Single center, single blind, prospective, randomized phase II controlled, to be conducted without crossover with patients recruited over a 2 year period
Study agents:	Biocompatibles LC Bead ( Beads + doxorubicin ), 100-300 microns, 150 mg doxorubicin per procedure with additional 100-300 micron and larger size beads (Bead Block) as necessary to achieve stasis  Bead Block ( Beads ) microsphere, 100-300 micron with additional larger size beads as necessary to achieve stasis
Limitations of Study	LC Bead and Bead Block are both tinted blue. Because doxorubicin is red, the addition of doxorubicin to the embolization microspheres will change the color of the spheres to some degree, and thus it may be possible for the interventional radiologist performing the embolization to differentiate between the two embolics. All other participants performing image and data analysis will be blinded.
Enrollment:	100 patients will be enrolled, 50 in each study arm
Clinical site:	Memorial Sloan-Kettering Cancer Center, NY, NY
Primary endpoint:	Response to treatment by RECIST criteria
Secondary endpoints:	

• Tumor necrosis

• Toxicity

• Time to progression

• Survival

Safety endpoint:	The safety endpoint will be treatment related Serious Adverse Event (SAE) rate, defined by SAE occurring within 30 days of a procedure. SAE is defined as a grade 3 or 4 adverse event using the Common Terminology Criteria for Adverse Events (CTCAE) 3.0.
Primary analysis:	Intent-to-treat analysis
Secondary Analysis:	Per protocol analysis and treated population analysis
Principle Investigator:	[name]

Member  
Department of Radiology  
Memorial Sloan-Kettering Cancer Center  
[name]  
[name]

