## 2.0 OBJECTIVES AND SCIENTIFIC AIMS

### **Primary Objective**

In this study one group of patients with hepatocellular cancer (HCC) will undergo hepatic arterial embolization using microscopic beads + doxorubicin and another group with the microscopic beads alone. Response to treatment will be determined in each group by conventional RECIST criteria. Since there is no historical data on imaging response to treatment for either group, the

study will be randomized. The primary objective will be to estimate the response rate in the two arms.

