Although trans-arterial chemoembolization (TACE) has become the standard treatment for patients with unresectable HCC, there has never been convincing evidence that the chemotherapy used for TACE remains in prolonged contact with the tumor in high concentration, or that there is any difference in survival when chemotherapy is added to the embolization agents. With the recent availability of drug eluting beads that have been shown to result in high local concentrations of chemotherapy (LC Bead) when used for embolization of HCC, it is possible to perform a study that evaluates the specific role of a chemotherapeutic agent (doxorubicin) delivered intra-arterially for the treatment of HCC. The results of this study are intended primarily to estimate response to treatment within the study and control groups. They may also help to clarify the role of chemotherapy when added to the ischemic effect of arterial embolization. A substantial difference in response to treatment would serve as a signal that the doxorubicin eluting bead may improve outcome in patients with HCC, and warrants further study. Coupled with an increase in TTP or survival, this might serve as the basis for an appropriately powered phase III trial. In addition, this study may validate a new imaging technique for evaluating response to treatment, and indicate if this imaging response to treatment may be used as a surrogate biomarker for outcome.

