## **14.0 BIOSTATISTICS**

This primary objective of this study is to estimate the response rates (CR + PR) to treatment following hepatic arterial embolization of hepatocellular cancer (HCC) using microscopic beads + Doxorubicin and beads alone by conventional RECIST criteria. With 50 patients in each arm response rates can be estimated to within +/- 14%. Patients will be randomly assigned to one the two treatment arms. A two-arm study was deemed necessary because there was not sufficient preliminary data on the control arm to design a single-arm study with historical controls. This is not a study where the goal is to test a hypothesis, rather the emphasis is on the estimation of response rates in the two arms. For this reason the sample size justification is provided in terms of the precision (half length of the asymptotic confidence interval) of these estimates instead of a power calculation. This is in the same spirit with most randomized Phase II trials of chemotherapeutic agents.

Randomization will be performed using the Clinical Research Database (CRDB), the central computing facility for clinical research at MSKCC. This system will generate a treatment assignment using the method of permuted blocks, at the time the patient is registered. Due to the nature of the treatment, the interventional radiologist will not be blinded but the radiologists assessing response to treatment will be blinded to treatment assignment.

One of the secondary objectives is to quantify the amount of necrosis in the two treatment arms and correlate this with conventional RECIST response as well as time to progression. With 50 patients in each arm, percent necrosis can be estimated to within +/- 14% of its standard deviation. Using 50% necrosis as threshold we plan to evaluate the degree of agreement between RECIST and necrosis response using Cohen's kappa and McNemar's test.

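### The signal for further study is a between-arm difference in response, but estimates and precision are planned only for each arm separately; adding the difference with its interval is a cheap improvement

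*Combined protocol and SAP*

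**What the plan says.** The stated use of the response result is in Section 3.0, under Preliminary Data: "A substantial difference in response to treatment would serve as a signal that the doxorubicin eluting bead may improve outcome". The sentence goes on to say that this would justify more study. The next sentence adds the later step: "Coupled with an increase in TTP or survival, this might serve as the basis for an appropriately powered phase III trial". No size is attached to the word substantial.

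The planned analysis is in Sections 2.0 and 14.0. The primary objective reads "The primary objective will be to estimate the response rate in the two arms". Section 14.0 explains the choice (the quote stops just before both arms are named): "This is not a study where the goal is to test a hypothesis, rather the emphasis is on the estimation of response rates in the". Accordingly, the number of patients is justified by the half-width of the asymptotic interval for each rate, and not by power. The precision given is "With 50 patients in each arm response rates can be estimated to within +/- 14" percent, and Section 1.0 fixes the size: "100 patients will be enrolled, 50 in each study arm".

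The log-rank test in Section 14.0 is the one formal comparison of the arms. It concerns time to progression and survival, both secondary. Nothing in the documents plans an estimate, an interval or a stated precision for the difference in response rates.

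**The concern.** The quantity that is planned and the quantity that will be interpreted are not the same. Section 14.0 will deliver two response rates, each with its own interval. Section 3.0 reads the signal from the contrast between them. A difference between two independent proportions is less precise than either one: when the rates are equal, its standard error is √2 (about 1.4) times that of one arm. The only response precision in the protocol, 14 points, therefore does not describe the comparison that Section 3.0 has in mind.

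What is at stake is how the result is read. Without a planned interval for the difference, and with no size given for substantial, a chance gap of 10 to 15 points could be taken as a signal. How much weight to give an observed gap would also be settled after the data are seen.

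**Working it through.** **Inputs**
- 50 patients per arm (Sections 1.0 and 14.0).
- Half-width of the asymptotic interval for one arm: 14 points (Section 14.0).
- Confidence level: not stated; 95% two-sided is assumed.
- Response rates: Section 2.0 says there are no historical imaging-response data for either group, and no expected rate is given. A range of 10% to 50%, equal in both arms, is assumed.

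**Step 1: reproduce the plan's figure.** Half-width for one arm = 1.96 × √[p(1−p)/50]. At p = 0.5 this is 1.96 × √(0.25/50) = 0.1386, or 13.9 points, which rounds to the stated 14. A 90% level would give 11.6 points and does not match, so 95% at the worst-case rate is the likely basis.

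**Step 2: the same formula for the difference.** Half-width = 1.96 × √[2p(1−p)/50]. At p = 0.5 this is 1.96 × √(0.50/50) = 0.196.

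| Assumed rate, both arms | One arm, ± points | Difference, ± points |
|---|---|---|
| 10% | 8.3 | 11.8 |
| 20% | 11.1 | 15.7 |
| 30% | 12.7 | 18.0 |
| 50% | 13.9 | 19.6 |

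**Step 3: how often chance alone produces a gap.** Take X and Y as independent binomial counts with n = 50 and the same p. The probability that the doxorubicin arm has at least k more responders is Σₓ P(X = x) × P(Y ≥ x + k). A gap of at least 10 points means k = 5. A gap of at least 15 points is 7.5 patients, so k = 8. A gap of at least 20 points means k = 10. The cut-offs are illustrations, because the protocol defines none.

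| True rate, both arms | ≥10 points | ≥15 points | ≥20 points |
|---|---|---|---|
| 10% | 6.6% | 0.6% | 0.1% |
| 20% | 13.0% | 3.0% | 0.9% |
| 30% | 16.3% | 5.1% | 1.9% |
| 50% | 18.4% | 6.7% | 2.8% |

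**Step 4: what a planned interval would show.** Observed rates of 10% and 20% give a difference of 10 points with half-width 1.96 × √(0.09/50 + 0.16/50) = 13.9 points, so the interval runs from −3.9 to 23.9. Observed rates of 30% and 50% (15/50 and 25/50) give 20 points, with a simple asymptotic interval of 1.2 to 38.8 and a Newcombe interval of 0.8 to 37.2. In both cases the interval for the difference states directly how much the gap can bear.

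**The case against.** The strongest reply is that per-arm estimation is a deliberate and disclosed choice. Section 14.0 says so, Section 2.0 sets the same objective, and Section 3.0 itself says that the results are mainly meant to estimate response within each group. The 14 points are labelled as the precision of response rates and are never offered as the precision of a difference. All of this stands: there is no arithmetic error, and the absence of a power calculation for response is not the fault. But an interval for a difference is also estimation, so adding it fits the stated aim.

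A second reply is that anyone can compute the interval from the two reported counts. That is true, and it is why the point is small. Planning it in advance still fixes how the signal is read before the data are known, and puts the right precision next to the stated use.

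Two stronger readings are tempting, and the documents support neither. A reader might infer that the response difference alone decides whether phase III goes ahead. Section 3.0 couples it with an increase in time to progression or survival and words the step as a possibility; the protocol has no go/no-go rule. A reader might also infer that the arms are to be judged by whether their separate intervals overlap. Nothing in the protocol says that.

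Finally, the chance figures depend on the assumed rate and cut-off. At low response rates, or if substantial means 20 points or more, chance gaps are uncommon. Low rates cannot be ruled out, since Section 3.0 notes that RECIST takes no account of necrosis.

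**Conclusion.** The point holds as a cheap improvement, not as a flaw in the primary analysis. Section 3.0 intends to read a signal from a between-arm difference in response for which Section 14.0 plans neither an estimate nor an interval. The precision of that difference is between 11.8 and 19.6 points over assumed rates of 10% to 50%, against the 14 points quoted for a single arm at its worst case. With no true difference, an advantage of at least 10 points for doxorubicin would appear in about 7 to 18% of trials, and of at least 15 points in about 1 to 7%. These sizes rest on a 95% level, equal rates in the two arms, all 50 patients per arm being evaluable, and illustrative cut-offs. The per-arm estimates and their stated precision are unaffected.

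**What to change.** In Section 14.0, add the between-arm difference in RECIST response rate (doxorubicin arm minus bead arm) with a 95% interval, for example by Newcombe's method, and state its expected half-width: up to about 20 points with 50 per arm. State the 95% level for the per-arm intervals as well. In Section 3.0, say that the signal for further study will be read from that difference and its interval.

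The cost is a few lines of text. No hypothesis test, change in sample size or additional data is needed. The one drawback is that the precision stated for the comparison will look less favourable than the 14 points now quoted.
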